6.3.2. Medical History Diagnosis Dates

If the onset date of any medical history diagnosis is only partially available, the first of the month will be imputed for any missing days and January will be imputed for any missing months. Imputed dates will be used to derive study day and will not be presented in the data listings. Any missing dates will be presented as "UNK" in the listing.

6.3.3. Medication Dates

For prior and concomitant medications with incomplete dates, the following rules will be used to impute start and/or stop dates for the purposes of determining if a medication is prior or concomitant only. Imputed dates will not be presented in the data listings.

For partial start dates:

- If day is missing, and the month and year match the month and the year of the first dose date, the medication start day will be imputed as the day of first dose. Otherwise, the first of the month will be used.
- If month is missing and the year matches the year of the first dose date, the medication start month and day will be imputed as the month and the day of the first dose date. Otherwise, January 01 will be used.
- If the start date is completely missing, the start date will not be imputed.
- If the stop date is complete and the imputed start date is after the actual stop date, then the start date will be imputed as the stop date.

For partial stop dates:

- If the day is missing, then the last day of the month will be used.
- If the month and day are missing, then December 31 will be used.
- If the stop date is completely missing then the date of last study participation date will be used.

6.3.4. Adverse Events

6.3.4.1. *Missing dates*

The following rules will be used to impute start and/or stop dates for adverse events with incomplete dates, in order to determine whether an AE is treatment-emergent or not. Imputed dates will not appear in the data listings.

Adverse events with partial start dates:

- If AE start day is missing, and the month and year match the month and the year of the first dose date, the day of the first dose date will be imputed. Otherwise, the first of the month will be used.
- If AE start month is missing, and the year matches the year of the first dose date, the month and the day of the first dose date will be imputed. Otherwise, January 01 will be used.
- If the AE start date is completely missing, the AE will be imputed to the first dose date.

• If the AE stop date is complete and the imputed AE start date is after the AE actual stop date, then the AE start date will be imputed as January 01 of the same year as the AE stop date.

6.3.4.2. Other missing information

Any missing severity assessments for AEs will be imputed as "severe" and any missing relationship to study medication will be considered "related" for summary purposes. The imputed values will not be presented in the listing.

6.3.5. Efficacy Assessments

Missing data may arise due to subjects missing some assessments (intermittent missingness), or as a result of subject dropouts and not being available for subsequent assessments (monotone missingness).

The primary analysis via the general linear model with random effects (also called Mixed Model with Repeated Measures (MMRM)) uses all available data and assumes that the missing data due to dropouts are missing at random (MAR). The Kenward Roger method is used to calculate the denominator degress of freedom and adjust standard errors for the test of fixed effects. In order to assess the impact of missing data due to dropouts on the inference for the co-primary endpoints, a sensitivity analysis will be performed where data after dropout will be imputed using multiple imputation and the statistical analysis via MMRM will be repeated with the filled in data. Details on the multiple imputation is described in Section 8.1.1.3.

6.4. Visit Windows

All data will be summarized according to the scheduled visit and time points as outlined in the protocol and by the visit denoted on the electronic case report form (eCRF). The unscheduled, end-of-treatment (EOT) and early termination (ET) visit will be mapped to a scheduled visit for analysis using the date of collection/assessment and Day 1, first dose date, as a basis to determine study day and then study day will be mapped to the intended visit according to the visit windows specified in the table below. Unscheduled visits after EOT visit date, including ET visit, will be windowed using relative days since last dose date; the mapping will follow the table below. In order to accommodate as much data as possible into analysis, these windows have been widened compared to protocol-specified operational window, to have no gap between them (exception: UPSIT, Lund-MacKay scores; See Table 2e); these windows are used for analyses purpose only. Data collected weekly (i.e., EQ-VAS) or daily (i.e., nocturnal awakenings, nasal peak inspiratory flow [NPIF]) will be mapped to the analysis week starting from Day 1, Week 1 through Week 24 using the date of collection/assessment.

Once analysis visit windows are assigned, all visits, including scheduled visits, unscheduled visits, and ET visits will be eligible for being flagged as the "analyzed record" within the analysis window. A subject's individual analysis visit window could potentially contain more than 1 visit. In the event of multiple visits falling within an analysis window or in case of a tie, the following rules will be used in sequence to determine the "analyzed record" for the analysis visit window:

- If there is a scheduled visit/day for the analysis visit window, then the scheduled visit/day data will be used.
- If there is no scheduled visit/day for the analysis visit window, the data closest to the scheduled day/time (i.e., target day) will be used. Exception: Week 24/EOS/ETV visit will use the last observation in the visit window, instead of the closest data.

• If there is no scheduled visit/day for the analysis visit window and there is a tie between the data in the number of days/hours before and after the scheduled day, the later data will be used.

The summary by visit will use "analyzed records" only ---at most one per subject per parameter.

An unscheduled visit that does not fall under any window will remain in the database and will be included in the listings. The data not flagged as the "analyzed record" will be included in subject listings. Tables 2a to 2f display visit windows for multiple analyses.

Table 2a: Visit Windows for Assigning ET Visits to an Analysis Visit for Nasal Endoscopy, SNOT-22, QoL, Nasal Polyps Resource Questionnaire, and ACQ-7

Study Period	Analysis Visit	Target Day	Window for Reassignment to Analysis Visit
Baseline	Baseline	1	≤ 1
Treatment Period	Week 4	29	2-42
	Week 8	57	43-70
	Week 12	85	71-98
	Week 16/EOT	113	99-126
Safety Follow-up Period	Week 24/EOS/ETV**	169	127-182

**The last observation in the time window will be used. [This is an exception from the rule regarding closest to target.]

Table 2b: Visit Windows for Assigning ET Visits to an Analysis Visit for Spirometry

Study Period	Analysis Visit	Target Day	Window for Reassignment to Analysis Visit
Baseline	Baseline	1	≤1
Treatment Period	Week 4	29	2-42
	Week 8	57	43-70
	Week 12	85	71-98
	Week 16/EOT**	113	99-126

**The last observation in the time window will be used. [This is an exception from the rule regarding closest to target.]

Table 2c: Visit Windows for Assigning ET Visits to an Analysis Visit for Hematology and Chemistry

Study Period	Analysis Visit	Target Day	Window for Reassignment to Scheduled Analysis Visit
Baseline	Baseline	1	≤1
Treatment Period	Week 1	5	2-10
	Week 4	29	11-42
	Week 8	57	43-70
	Week 12	85	71-98
	Week 16	113	99-126
Safety Follow-up Period	Week 24/EOS/ETV**	169	155-182

**The last observation in the time window will be used. [This is an exception from the rule regarding closest to target.]

Study Period	Visit	Target Day	Window for Reassignment to Scheduled Visit
Baseline	Baseline	1	≤ 1
Treatment Period	Week 4	29	2-42
	Week 8	57	43-70
	Week 12	85	71-98
	Week 16/EOT	113	99-126
Safety Follow-up Period	Week 20	141	127-154
	Week 24/EOS/ETV**	169	155-182

Table 2d: Visit Windows for Assigning PW Visits to an Analysis Visit for Immunogenicity and Vital Signs

**The last observation in the time window will be used. [This is an exception from the rule regarding closest to target.]

Table 2e: Visit Windows for Assigning PW Visits to an Analysis Visit for UPSIT and Lund-MacKay Scores

Study Period	Visit	Target Day	Window for Reassignment to Scheduled Visit
Baseline	Baseline	1	≤1
Treatment Period	Week 8*	57	43-84
	Week 16/EOT	113	85-126

*UPSIT only. Lund-MacKay score is not assessed at Week 8.

**UPSIT and Lund-MacKay scores do allow gaps between analysis visits.

Table 2f: Visit Windows for Assigning PW Visits to an Analysis Visit for EQ-VAS, Nocturnal Awakenings, and NPIF

Study Period	Visit	Target Day*	Window for Reassignment to Scheduled Visit
Baseline	Baseline	1	≤ 1
Treatment Period	Week 1	5	2-7
	Week 2	11	8-14
	Week 3	18	15-21
	Week 4	25	22-28
		•••	
	Week 16/EOT	102	99-105
Safety Follow-up Period	Week 20	130	127-133
	Week 24/EOS/ETV**	158	155-161

*Except for Week 1, Target Day for the rest weekly analysis visits is the mid-week day.

**The last observation in the time window will be used. [This is an exception from the rule regarding closest to target.]

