8.1.8.2 EUROPEAN QOL SCALE (EQ-5D)

The EQ-5D is a standardized health-related QoL questionnaire developed by the EuroQol Group in order to provide a simple, generic measure of health for clinical and economic appraisal and inter-disease comparisons. The EQ-5D is designed for self-completion by subjects and takes only a few minutes to complete.

The EQ-5D was used to study the impact on QoL for filgrastim administration in CRS patients, the scores improved though they were not statistically significant (*Van Agthoven et al., 2001*).

The EQ-5D descriptive system comprises 5 dimensions: mobility, self-care, usual activities, pain/discomfort and anxiety/depression. Each dimension has 5 levels: no problem, some problems, severe problems. The EQ VAS records the respondent's self-rated health on a vertical visual analogue scale. The EQ VAS 'thermometer' has endpoints of 100 (Best imaginable health state) at the top and 0 (Worst imaginable health state) at the bottom.

The EQ-5D will be completed as indicated in the SoA (see Section 1.3) and is located on the clinical tablet.

A sample EQ-5D is provided in Appendix G.

8.1.8.3 7-ITEM ASTHMA CONTROL QUESTIONNAIRE (ACQ-7)

The ACQ-7 will be used in this study to assess the asthma symptoms (nocturnal waking, symptom on waking, activity limitation, and shortness of breath, wheezing, and short acting β agonist [SABA] usage) and FEV₁ measurement in subjects with active asthma disease. Subject will be asked to recall their

experiences during the previous week by responding to 5 symptom related questions and 1 question related to bronchodilator use. Questions will be scored from 0 (totally controlled) to 6 (severely uncontrolled). The questionnaire will be administered only in subjects with active asthma disease. The subject should complete the ACQ 7 at the time points indicated in the SoA (see Section 1.3) and is located on the clinical tablet.

A sample ACQ-7 is provided in Appendix H.

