Change from baseline to Week 16 in PM NPIF	MMRM, including the change from baseline in PM NPIF as the dependent variable; treatment group, stratification factor, time (Weeks 4, 8, 12, and 16), treatment by stratification factor, and treatment by time interaction as fixed effect factors; baseline PM NPIF score as covariate; and subject as a random effect	
Change from baseline to Week 16 in bilateral endoscopic NPS in subjects with comorbid asthma	MMRM including the change from baseline in NPS as dependent variable; treatment group, time (Weeks 4, 8, 12, and 16), and treatment by time interaction as fixed effect factors; baseline NPS score as covariate; and subject as random effect	
Change from baseline to Week 16 in SNOT-22 in subjects with comorbid asthma	MMRM as above for NPS will be applied for SNOT- 22 score	
Change from baseline to Week 16 in the percent of 3-dimentional volumetric maxillary sinus occupied by disease (%VMSOD) as assessed by CT scan	Analysis of covariance (ANCOVA) modeling the change from baseline in %VMSOD score at Week 16 as dependent variable; baseline %VMSOD score as covariate; and treatment as a factor	
Change from baseline to Week 16 in SF-36 physical component summary (PCS)	MMRM including the change from baseline in SF-36 PCS score as dependent variable; treatment group, stratification factor, time (Weeks 4, 8, 12, and 16), treatment by stratification factor, and treatment by time interaction as fixed effect factors; baseline SF-36 PCS score as covariate; and subject as a random effect	
Change from baseline to Week 16 in SF-36 mental component summary (MCS)	MMRM as above for SF-36 PCS will be applied for SF-36 MCS	

Endpoint	Statistical Analysis Methods
Change from baseline to Week 16 in EQ-5D index score	MMRM including the change from baseline in EQ-5D index score as dependent variable; treatment group, stratification factor, time (Weeks 4, 8, 12, and 16), treatment by stratification factor, and treatment by time interaction as fixed effect factors; baseline EQ-5D index score as covariate; and subject as a random effect
Change from baseline to Month 4 in VAS	MMRM including the change from baseline in VAS score as dependent variable; treatment group, stratification factor, time (Months 1, 2, 3, and 4), treatment by stratification factor, and treatment by time interaction as fixed effect factors; baseline VAS score as covariate; and subject as a random effect

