8.3.1.2. European Quality of Life Scale (EQ-5D)

The impact of CRSwNP on the quality of life of the patient will be assessed using the EQ-5D questionnaire. This questionnaire has two components: health state description and evaluation.

In the description part, the EQ-5D-5L health questionnaire is a health-related quality of life instrument with 5 dimensions: mobility, self-care, usual activities, pain/discomfort, and anxiety/depression. Each dimension has 5 possible levels: no problems, slight problems, moderate problems, severe problems and extreme problems.

The summary of results will follow the EQ-5D-5L guidelines for results presentation. For the "Health Profiles" descriptive system summary results will show the number, and proportion (%) of subjects in each Item score (No Problems, Slight Problems, Moderate Problems, Severe Problems, Extreme Problems) by treatment at baseline and at each visit (Weeks 4, 8, 12, and 16).

No formal statistical testing will be carried out for the EQ-5D-5L.

In the evaluation part, the EQ-VAS measures overall self-rated health status on a 0-100 scale, with 0=worst health you can imagine and 100=best health you can imagine. Thus higher scores are suggestive of better health status.

Summary statistics will be presented for the EQ-VAS score showing number of subjects, mean, standard deviation, median, minimum and maximum for each treatment group at baseline and each visit (Weeks 4, 8, 12 and 16), and change from baseline.

An MMRM with the baseline EQ-VAS score as covariate, and treatment (3 levels), stratification factor, treatment by stratification factor, categorical time point (Weeks 4, 8, 12, and 16), and treatment by time interaction as fixed effect factors, and subject as a random effect will be used to obtain least squares estimates for the change from baseline in EQ-5D VAS score in Week 16 for each treatment group. Each etokimab dose group will be compared to the Placebo group using the Week 16 least squares means and standard errors obtained from the model. Associated 95% confidence limits for the LS means and p-values for the treatment comparisons will be displayed.

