8.3.1.3. Patient Related Rhinosinusitis Severity Using Visual Analog Scale (VAS)

The Visual Analogue Scale (VAS) for rhinosinusitis is used to evaluate the total severity. The patient is asked to indicate on a continuous scale (VAS) the answer to the question: "How troublesome are your symptoms of rhinosinusitis?" The VAS score ranges from 0 (Not troublesome) to 10 (Worst thinkable troublesome).

The disease severity can be divided into MILD, MODERATE and SEVERE based on total severity visual analogue scale (VAS) score (0 to 10 cm):

- MILD = VAS 0-3
- MODERATE = VAS >3-7
- SEVERE = VAS >7-10

The VAS is administered weekly via an electronic diary device. On Day 1, the eDiary is presented to the subject prior to dosing and the subject must complete the VAS scale before receiving study drug.

The value obtained on Day 1 is the subject's baseline value.

Summary statistics for the VAS for Day 1 and the following weeks until Week 24 will include n, mean, standard deviation, median, minimum and maximum for baseline, the time of measurement, and the change from baseline.

Statistical analysis for the change from baseline in VAS scores at Weeks 4, 8, 12, and 16 will be modeled using an MMRM with baseline VAS score as covariate, and treatment (3 levels), stratification factor, treatment by stratification factor, categorical time (Weeks 4, 8, 12, and 16), and treatment by time interaction as fixed effect factors, and subject as a random effect included in the model. Treatment comparisons will be based on the Week 16 least squares means and standard errors. Associated 95% confidence limits for the LS means and the p-value for comparison of each etokimab dose group with the Placebo group will be displayed.

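### SAP 6.4 and Table 2f name the clinic-visit EQ-VAS as the weekly scale; applied as printed, on-target EQ-VAS visits miss their windows, and the true weekly scale, the rhinosinusitis VAS, is named in no window table

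*SAP*

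**What the plan says.** SAP 6.4 (Visit Windows) classes the EQ-VAS as weekly data: "Data collected weekly (i.e., EQ-VAS) or daily (i.e., nocturnal awakenings, nasal peak inspiratory flow [NPIF]) will be mapped to the analysis week". The table it points to repeats the name: "Table 2f: Visit Windows for Assigning PW Visits to an Analysis Visit for EQ-VAS, Nocturnal Awakenings, and NPIF".

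Other sections describe the scales differently.

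- **EQ-VAS.** Protocol 8.1.8.2 makes it part of the EQ-5D: "The EQ VAS records the respondent's self-rated health on a vertical visual analogue scale". The EQ-5D is done on the clinical tablet. The schedule of activities places it, under a QoL row shared with the SF-36, at Day 1 and Weeks 4, 8, 12, 16 and 24. SAP 8.3.1.2 models the EQ-VAS at Weeks 4, 8, 12 and 16 and compares arms at Week 16.
- **Rhinosinusitis VAS.** SAP 8.3.1.3 states: "The VAS is administered weekly via an electronic diary device". Protocol 8.1.8.7 agrees. The SAP models this scale at the same four weeks and also asks for weekly summaries up to Week 24.

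The scales run in opposite directions: EQ-VAS is 0-100 with higher better, and the rhinosinusitis VAS is 0-10 with higher worse.

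Table 2a, the window table for clinic-visit data, lists QoL. None of Tables 2a to 2f names the rhinosinusitis VAS.

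**The concern.** Table 2f is built for diary weeks, each seven days long. Clinic visits are targeted one day after a diary week ends (Day 29 against Days 22-28, for example). A clinic-visit item put through diary-week windows will therefore tend to fall into the following week, which the four-visit model does not use.

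Two Week 16 comparisons are affected. For the EQ-VAS, a programmer following the text would drop on-schedule values. For the rhinosinusitis VAS, no table states which weekly diary entry counts as Week 4, 8, 12 or 16. That matters more because Protocol Table 3 planned this scale by month (Months 1 to 4) and the SAP moved it to weeks.

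**Working it through.** **Inputs**

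- Permitted visit days (schedule of activities): Week 4 = 29 ± 3, Days 26-32; Week 8 = 57 ± 3, Days 54-60; Week 12 = 85 ± 3, Days 82-88; Week 16 = 113 ± 5, Days 108-118.
- Table 2f as printed: Week 2 = Days 8-14, Week 3 = 15-21, Week 4 = 22-28, Week 16 = 99-105 with target Day 102. Weeks 5 to 15 are elided.
- Table 2a: Week 4 = Days 2-42, Week 8 = 43-70, Week 12 = 71-98, Week 16 = 99-126.

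**Step 1: reproduce Table 2f.** The printed early rows follow Week k = Days (7k − 6) to 7k, and the footnote sets the target: "Except for Week 1, Target Day for the rest weekly analysis visits is the mid-week day". For k = 2, 3 and 4 this gives 8-14, 15-21 and 22-28, as printed. For k = 16 it gives 106-112. The printed 99-105 is 7 × 15 − 6 to 7 × 15, which is Week 15. The rows from Week 16 on are thus one week early. As a check, Days 29-98 hold 70 / 7 = 10 weeks, but Weeks 5 to 15 are 11 weeks.

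**Step 2: count permitted clinic days inside each window.**

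| Visit | Permitted days | Table 2f window | Days that qualify | Target day inside? | Table 2a |
|---|---|---|---|---|---|
| Week 4 | 26-32 | 22-28 (printed) | 26-28: 3 of 7 | Day 29: no | 7 of 7 |
| Week 8 | 54-60 | 50-56 (inferred) | 54-56: 3 of 7 | Day 57: no | 7 of 7 |
| Week 12 | 82-88 | 78-84 (inferred) | 82-84: 3 of 7 | Day 85: no | 7 of 7 |
| Week 16 | 108-118 | 99-105 (printed) | 0 of 11 | Day 113: no | 11 of 11 |
| Week 16 | 108-118 | 106-112 (slip corrected) | 108-112: 5 of 11 | Day 113: no | 11 of 11 |

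At Week 16 as printed, the first permitted day is 108 − 105 = 3 days after the window closes.

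The Week 8 and 12 rows are inferred from the 7-day pattern. Since the slip lies somewhere between Weeks 4 and 16, the windows actually intended there cannot be read from the table.

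**Step 3: separate the two causes.** Correcting the slip moves Week 16 from 0 to 5 of 11. The other 6 of 11 (Days 113-118, including the target) stay outside because a diary week ends on Day 112. That remainder comes from using diary weeks for a clinic-visit item.

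**Step 4: the EQ-5D analysis.** Protocol 9.4.2, Table 3 plans a repeated-measures model for "Change from baseline to Week 16 in EQ-5D index score". SAP 8.3.1.2 says "No formal statistical testing will be carried out for the EQ-5D-5L" and applies the model to the EQ-VAS. SAP Section 12 records only the change to nocturnal awakenings.

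**The case against.** **A naming slip.** The schedule contains one weekly VAS, so EQ-VAS in SAP 6.4 is probably a mislabel for the rhinosinusitis VAS. On that reading the weekly scale takes Table 2f, the EQ-VAS takes the QoL rows of Table 2a, and no EQ-VAS value is lost. This is the likeliest intention, but it is an inference. The wrong name appears in both the text and the table title.

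**The visit label governs.** SAP 6.4 opens by summarising data by scheduled eCRF visit, and date mapping is introduced for unscheduled, end-of-treatment and early-termination visits. On that rule, scheduled Week 4, 8 and 12 records may keep their label. This stands as an ambiguity. It does not clearly rescue Week 16, because end-of-treatment visits are among those mapped by date, and the later sentence sends the EQ-VAS to date mapping by name. The preference for a scheduled visit operates only among records already inside a window.

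**Table 2a covers both scales.** SAP 4.3.1 lists the rhinosinusitis VAS under quality of life, so Table 2a's QoL label could be stretched to it, and the closest-to-target rule would pick an entry. It would be wrong to say that no rule could apply. The fit is poor, though: Table 2a has no weekly rows and its Week 4 spans Days 2-42. For the EQ-VAS, the same label means two conflicting Week 16 windows, Days 99-126 and Days 99-105.

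**Stronger readings.** A reader might infer that the mislabel alone empties Week 16. It does not; the zero also needs the one-week slip. A reader might also turn the day counts into percentages of values lost. That requires the spread of visits over the permitted days, which the documents do not give.

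**Conclusion.** The scale is misnamed, and the printed rule gives a wrong result for the EQ-VAS. If Table 2f is applied to it by date, target Day 29 misses Week 4 (3 of 7 permitted days qualify) and target Day 113 misses Week 16 (0 of 11 as printed, 5 of 11 with the slip corrected). These counts need no assumption about when visits occur. They do assume that Table 2f overrides both Table 2a and the opening visit rule of SAP 6.4, an order of precedence the SAP does not settle. The Week 8 and 12 counts of 3 of 7 are inferred only.

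The rhinosinusitis VAS is named in no window table, and the one label that might cover it does not suit weekly data.

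Both scales are exploratory and outside the testing hierarchy, so no co-primary or secondary result is affected. The point is still worth correcting, since the SAP plans Week 16 p-values for both.

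The move from the EQ-5D index score to the EQ-VAS is a separate, minor documentation gap. Protocol 9.4.2.2 leaves full details of exploratory analyses to the SAP, and the SAP states its choice openly; only the entry in Section 12 is missing.

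**What to change.** 1. In SAP 6.4 and the Table 2f title, replace EQ-VAS with rhinosinusitis VAS.
2. State that the EQ-5D, including the EQ-VAS, uses Table 2a. All 7 permitted days at each of Weeks 4, 8 and 12, and all 11 at Week 16, then qualify.
3. Correct the later rows of Table 2f to its own 7-day pattern: Week 16 = Days 106-112 (mid-week Day 109), Week 20 = 134-140 (Day 137), Week 24 = 162-168 (Day 165). Print the elided rows. This correction also serves NPIF and nocturnal awakenings, which share the table.
4. Record in SAP Section 12 that the protocol's EQ-5D index-score model was replaced by an EQ-VAS model.

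The cost is SAP wording only, with no new data.
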